### 4.0 Randomisation and Blinding

Randomization for treatment order will be conducted by computer generation by the statistical team to create a treatment order. A randomisation order will be generated by [name] (Biomathematics and Statistics Scotland) and participants will be assigned in the order in which they are assigned to the study following their health screening and

confirmation of eligibility. The randomisation uses a mathematical algorithm validated for generation of random sequences.

The study will be conducted in a non-blinded method with diets colour coded.

#### 5.0 Withdrawal Procedures

If any participant wishes to withdraw from the study at any point after recruitment, any data already collected with consent will be retained and used in the study. No further data will be collected, or any other research procedures carried out on or in relation to the participant after they withdraw. A "withdraw from study form" will be completed and attached to the participants record. Unless the participant specifically withdraws consent to use any data already collected, all data to the date of withdrawal will be retained and used for analysis purposes.

#### 6.0 Study and Safety Assessments

The risks associated with participation in this project are minimal. Minor risks are associated with the collection of blood samples.

Blood Collection: Blood collection will be performed by trained and experienced phlebotomists or research nurses. Venepuncture blood collection is not associated with risks greater than that associated with a routine blood test. There may be mild discomfort and a small amount of localised bruising as a result of blood collection and some participants may feel light headed or faint, but no more than is experienced with a routine blood test. Each member of the research team also has extensive experience in blood collection and handling. A phlebotomy checklist will be completed with each blood test to confirm any previous problems with blood tests recent blood donations and current illness to minimise risks.

Any medical values which fall outside of normal ranges will be reported to the HNU unit manager, recorded appropriately and the participant's GP notified (with consent). All measurements will be undertaken by trained research staff in accordance with authorised SOPS and nursing staff are on site to maintain subject health and safety. All adverse events will also be reported to the HNU unit manager and Sponsor.

#### 7.0 Data Collection and Management

All data will be collected by the research team and bloods collected by the phlebotomists or research nurse. Data will be collected using validated questionnaires, the collection of biological samples (blood, faeces), and measures of human physiology with calibrated research equipment. The research team are trained in the appropriate data collection methods and data collection will be completed according to authorised SOPS. All data will be stored in anonymised form in locked cabinets at the Rowett Institute in the Human Nutrition Unit or on secure shared drives accessible by the research team. Biological samples will be stored in secured 70°C degree freezers as until analysis. Data will be identifiable only by the research team in order to link health outcomes and samples to subjects. All electronic data will be stored "ad infinitum" on the University of Aberdeen central server. 16S rRNA gene-based gut microbiota profiling sequence data would need to be uploaded to a publicly accessible data repository such as the European Nucleotide Archive prior to publication. Only bacterial profiles will be available, and sample will remain anonymised so that these profiles cannot be linked to specific individuals. Archiving will only occur once all relevant paper data has been published. It is expected that paper data will be archived after 5 years following publication of the project; in line with the institutional retention schedule.

#### 8.0 Labs and Samples Analysis

Faecal samples will be used to determine gut microbiota, SCFA, VOCs and calprotectin. Samples will be collected into a pre-lined faecal collection pot when the participant needs to defecate. The participant will be required to seal the container and return it to the institute within 12 hours for effective microbial microbiome and metabolome profiling (e.g. bacterial 16S rRNA gene/SCFAs/VOCs analysis [9, 14, 15]. Calprotectin concentration in faeces is higher than in plasma and significantly increased levels of calprotectin in stool are found in patients with bowel inflammation (e.g. IBD), whereas it is not elevated in patients with nonorganic, rather functional diseases like irritable bowel syndrome (IBS) [16]. Blood samples will be collected by a trained phlebotomist or research nurse into 2 separate vacutainer tubes (EDTA and lithium hep tubes). Blood samples will be immediately spun in the centrifuge and plasma aliquots placed into Eppendorf tubes (insulin and TMAO (UOA) and hsCRP, sCD14, LPS binding protein (UOL)) and KONE cups (for glucose and lipid analysis). Plasma samples will be stored in a -70°C degree freezer until analysis.

All samples will be collected and stored in anonymised forms. All freezers are calibrated and monitored by the research team. All laboratory analysis of faecal and blood samples will be undertaken at the Rowett Institute by trained laboratory technicians in the analytical laboratories.

Samples will be stored until the study has been completed and then for further 5 years to allow for potential additional analysis in future ethically reviewed and approved studies. After this period, all samples will be destroyed.

#### 9.0 Statistics and Data Analysis

### 9.1 Sample Size Calculation

Emulsifier circulating bacterial DNA power calculation - The sample size chosen to give 80% power to exclude 50% increase in circulating bacterial DNA. Human studies to date have shown up to 10-fold increase in circulating bacterial DNA in CVD but a 50% increase, as has been demonstrated for example after an acute alcohol binge, is a more realistic expectation for the proposed human dietary study.

The largest published data set of peripheral venous blood bacterial 16S rRNA gene measurements is that published by Dinakaran *et al.* [17] who report data from 40 healthy controls and 80 patients with cardiovascular disease. Values for healthy controls for 16S rRNA genes were median 411.73 gene copy number per mL, IQR 186.62-617.16 (values for individuals with cardiovascular disease were more than ten times higher). By assuming that the mean was approximately similar to the median and extrapolating an approximate value for standard deviation (34/25x225=306) the power calculation shows that a sample size of 20 will give 80% power at P=0.05 of excluding a 50% increase in circulating bacterial DNA. Sample size for a paired or single sample Student t test.

Alpha = 0.05; Power = 0.8; Difference of mean from zero = 206; Standard deviation = 306 Estimated minimum sample size = 20 pairs; Degrees of freedom = 19 Allowing for drop out typical of volunteer dietary intervention studies, we would aim to recruit 22 volunteers for the study, to complete 20.

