### 1.2 Rationale for the study

This study primarily aims to determine whether short term (two week) high intake of lecithin alters gut function, as indicated by increased presence of bacterial DNA, soluble CD14 or LPS binding protein in the circulation (venous blood sampling), increased gut inflammation (faecal sampling for white blood cell components such as calprotectin), gut microbiota activity (faecal SCFA and bacterial DNA profile including estimation of diversity) and altered glucose metabolism (assessed by oral glucose tolerance test). This is achieved by comparing a low-emulsifier diet with a diet with soy lecithin emulsifier added – all food is provided to subjects as a controlled diet trial.

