### The Research Question

Does dietary intake of soy lecithin alter the intestinal lining and the microbes that normally exist in the intestinal lumen, in healthy subjects, consumed over a two-week period (in comparison to a low-emulsifier diet)?

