### 2.0 Study objectives and outcomes

### The Primary Objective:

Assessment of bacterial translocation by venous blood bacterial DNA in response to diet containing soya lecithin emulsifier, in comparison to control period of low-emulsifier diet. Measured as responding to pre and post dietary treatment as gene copy number per ml (as per Gutiérrez *et al.*, 2014 [6]), but using more validated universal qPCR primer sets (including total bacteria, phyla- and class-specific primers as described by Bacchetti De Gregoris *et al.*, 2011 [7]). These data will be backed up by measurement in venous blood of circulating soluble CD14 and LPS binding protein as additional markers of bacterial translocation [8] – see secondary endpoints.

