#### 9.2 Proposed Analysis

Data analyses will be reviewed by independent Statistician, [name] from BioSS, included as a subcontractor. The entire trial management team will be responsible for data analysis.

Missing Data - Data analysis will be performed using linear mixed models which enables the inclusion of all participants within the analysis even with missing time points. When entering data into excel spreadsheets, missing data will be left blank. Blank cells will be checked by statistician [name] during statistical analysis to confirm the data as uncollected/ erroneous as opposed to incorrectly transcribed.

The loss of data will be minimised by immediate saving of results on test days and storage of data on the University central server which is backed up daily. Consistent reminders to participants of study protocol, adherence to SOPs and calibration of equipment will be used to minimise the chances of errors.

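### Does describing the design as powered to exclude a 50% increase, beside a t test against zero, leave the sample size or the primary conclusion wrong?

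*Combined protocol and SAP*

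**What the plan says.** Section 9.1 uses the language of exclusion twice: first in stating the aim, "The sample size chosen to give 80% power to exclude 50% increase in circulating bacterial DNA", and again in stating the result, where 20 participants are said to give "80% power at P=0.05 of excluding a 50% increase in circulating bacterial DNA". The inputs listed below that are those of a paired or one-sample t test: "Difference of mean from zero = 206; Standard deviation = 306", with alpha 0.05, power 0.8 and 20 pairs. The same section says that a 50% increase "is a more realistic expectation for the proposed human dietary study", which treats it as the effect the team anticipates.

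Elsewhere the aim is framed as a question about difference. Section 1.2 says "This study primarily aims to determine whether short term (two week) high intake of lecithin alters gut function". The Research Question begins "Does dietary intake of soy lecithin alter the intestinal lining". The Primary Objective in section 2.0 compares the lecithin diet with the low-emulsifier control period and defines the measure thus: "Measured as responding to pre and post dietary treatment as gene copy number per ml". On analysis, section 9.2 says "Data analysis will be performed using linear mixed models which enables the inclusion of all participants within the analysis even with missing time points". It gives no margin, confidence-interval rule or statement about how a null result will be interpreted.

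**The concern.** Detecting an increase and excluding one are different inferential tasks. To detect it, one rejects zero. To exclude it, one shows that the confidence interval lies wholly below the increase in question. A test against zero that fails to reach significance does the first job unsuccessfully and does not, by that fact, do the second.

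Section 9.1 names the second task and calculates for the first. Because it pairs the word with the 0.05 level, a reader could take it to mean that p>0.05 would justify saying a 50% rise had been ruled out. This is the primary endpoint of a study of a widely used food additive, and a null result is plausible. If that reading were adopted, a trial whose interval still included a 50% increase could be reported as having ruled it out.

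**Working it through.** **Inputs, all from section 9.1.** n = 20 pairs (19 degrees of freedom), SD 306, difference 206, alpha 0.05, healthy-control median 411.73 copies/mL. Half of 411.73 is 205.9, hence 206. Sidedness is not stated. The two-sided test is the one that returns 20; a one-sided 0.05 test would need 16.

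**Reproducing the plan's figure.**
- Standard error = SD/√n = 306/√20 = 68.42.
- Noncentrality = 206/68.42 = 3.01.
- Two-sided power from the noncentral t distribution is 0.792 at n = 19 and 0.815 at n = 20.

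So 20 is the smallest number of pairs that reaches 80%, as stated.

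**The same design read as exclusion.** Take the rule to be that the upper limit of the two-sided 95% interval lies below 206. This is a one-sided 0.025 t test against 206, with noncentrality (206 − true difference)/68.42. At a true difference of zero this is again 3.01, so the probability is again 0.815. It falls if there is a small true increase:
- 0.63 at +10% (41.2 copies/mL)
- 0.40 at +20% (82.3 copies/mL)

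**What p>0.05 can and cannot say.**
- Expected 95% half-width = t(0.975, 19) × SE = 2.093 × 68.42 = 143.2 copies/mL, and 143.2/411.73 = 35%.
- Exclusion at that width needs an estimate below 206 − 143.2 = 62.8, and 62.8/411.73 = 15%.

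Estimates between about 63 and 143 copies/mL are therefore non-significant and still compatible with a 50% rise. The simulated probability of a trial that is non-significant and does not exclude 206 is:

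| True increase | SD 306 (plan) | SD 200 (assumed) | SD 433 (assumed) |
|---|---|---|---|
| 0 | 16% | 0.3% | 45% |
| +10% | 29% | 1.6% | 57% |
| +20% | 39% | 3.5% | 65% |

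The documents give no assumed true difference for an exclusion claim, so the rows are illustrative. So are the outer two columns. The 306 is extrapolated from the spread between people in another study, not from the within-person contrast analysed here, and the shares move strongly with it.

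**If the true increase is 50%.** 1 − 0.815 = 18.5% of trials are non-significant. That is the design's ordinary type II error. It becomes a rate of false exclusion only if p>0.05 is taken as exclusion. Under the confidence-limit rule, false exclusion is 2.5%.

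**The case for a change.** The best case for acting is that the word appears twice, so it is hard to dismiss as a single slip. The equality of the two powers does not fully rescue it either. The equality needs a true difference of exactly zero and an upper-limit rule, and section 9.1 states neither. The repair would be cheap (two verbs and a sentence, or a short decision rule in section 9.2), and settling the interpretation before data are seen removes some freedom afterwards.

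Much of this stands. The wording is imprecise, the interpretation of a null result is unwritten, and p>0.05 alone would not rule out a 50% rise. What does not stand is the step from there to a defect in the plan. The harm needs an inference rule that appears nowhere in the documents, while the rationale, research question, primary objective and displayed test all point to detection.

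Writing in an exclusion rule at 206 copies/mL would bring a fresh problem. That figure is half of another study's median in healthy controls, whereas this trial enrols people with a BMI of 27 to 40 and uses different primer sets. If the control level here were 200 or 800 copies/mL (assumed values), 206 would be a rise of 206/200 = 103% or 206/800 = 26%, and the rule would not be testing a 50% increase.

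**Conclusion.** No change to the plan is needed. The sample size reproduces, and the stated 80% is correct for detecting 206 copies/mL at SD 306 (81.5%). It is equally correct for placing the upper 95% limit below 206 when the true difference is zero. Carrying out the plan as written produces no wrong number: the mixed model in section 9.2 can supply a between-diet estimate with its interval, and the interval itself shows whether a 50% increase remains plausible.

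What is left is a loose verb and an unstated convention, both of which a competent analyst resolves by reading the design as a test for a difference and reporting the interval. The 16% to 39% of trials that would be non-significant yet inconclusive about a 50% rise describes the precision of a 20-person study, not an error in it. Those shares rest on the plan's SD of 306 and on assumed true increases of 0 to 20%. Whether 306 suits the paired contrast is a separate question that this conclusion does not settle.

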### Secondary endpoints:

Changes in comparison to control (expressed as pre-post change per diet period)

- Faecal calprotectin (Store frozen ELISA @[name] Lab, UoL)
- Faecal volatile organics compounds [VOCs] (Store frozen GC-MS @[name] lab, UoL) [9].
- Faecal microbiota and DNA extraction (Process for SCFA and DNA extraction within 2 weeks, then store frozen bacterial 16S rRNA gene sequencing @[name] Lab, Rowett; UoA).
- Plasma highly sensitive C-reactive protein [hsCRP] (Store frozen ELISA @[name] Lab, UoL; T1,2,3,4 overnight fasted).
- Plasma soluble CD14 and LPS binding protein (Store frozen ELISA @[name] Lab, UoL; T1,2,3,4 overnight fasted).
- Plasma fasting blood glucose and up to 3 hours after OGTT (KONE, Rowett; T1,2,3,4 as Time 0, 30, 60, 90, 120 minutes).
- Plasma fasting lipid profile (KONE, Rowett UoA, T1, 2, 3, 4; overnight fasted)
- Plasma fasted insulin profile and up to 2 hours postprandial OGTT (KONE, Rowett UoA; T1,2,3,4 as Time 0, 30, 60, 90, 120 minutes).
  (with calculation of HOMA and Matsuda index as an estimate of insulin sensitivity [10]
- Plasma trimethylamine-N-oxide (TMAO) as a measure of cardiovascular risk [11] (Rowett UoA; T1,2,3,4 as overnight fasted).

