## 3.3 Study Visits

Subsequent study visits will consist of 4 test days when volunteers will be asked to fast overnight before presenting at the HNU. In total there will a baseline visit followed by 4 study visits representing pre-post each diet treatment.

For Test days 1,2,3,4 (Protocol Days 8, 22, 29 and 43; one 6ml EDTA tube and one 6ml LiHep tube and one 2.7ml Li-Hep tube, total 14.7ml whole blood)

 Participants are asked to bring a fresh (<16 h) faecal sample for SCFA and DNA extraction; lab staff to report Bristol stool chart (D8, D22, D29 and D43) & collect VOC.

- Cannulation for blood sampling (D8, D22, D29, D43)
  - $\circ$  T0 Lipid profile (2x200µl plasma), whole blood in LiHep tube 1
  - $\circ~$  T0 Glucose (2x200  $\mu$ l plasma), whole blood in LiHep tube 1
  - $\circ$  T0 Insulin (2x200µl plasma), whole blood in EDTA tube 1
  - T0 Trimethylamine-N-oxide (TMAO), (2x200µl plasma), whole blood in LiHep tube 1
  - $\circ~$  T0 plasma hsCRP (2.7ml whole blood, (2x100 $\mu l$  plasma), whole blood in EDTA tube 1
  - $\circ~$  T0 soluble CD14 and LPS binding protein (2x100 $\mu l$  plasma), whole blood in EDTA tube
  - $\circ$   $\,$  T0 bacterial DNA in sterile tube (1ml whole blood), whole blood in Li-Hep tube
- After ingestion of 75g glucose (Days 8, 22, 29 and 43; one 2.7ml EDTA tube and one 2.7ml LiHep tube for each timepoint, total 21.6ml whole blood)
  - T30, T60, T90, T120 Glucose (2 x 200µl plasma for each timepoint), whole blood in EDTA tube 2,3,4,5
  - T30, T60, T90, T120 Insulin (2 x 200µl plasma for each timepoint) whole blood in LiHep tube 2,3,4,5
- GI discomfort questionnaire [13] (Storey et al 2007, D8, D22, D29, D43)

Total blood is 36.3ml each test day (equivalent to 2 tablespoons) or 145.2 ml over the entire protocol (less than one blood donation). Subjects will receive reimbursement of travel expenses and a small gratuity (up to £50).

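### The SD of 306 behind the sample size uses a quartile-to-SD factor that is not the normal one; under normality the SD is about 319 and power at 20 pairs about 78%, on a within-person condition that section 9.1 does not state

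*Combined protocol and SAP*

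**What the plan says.** Section 9.1 (Sample Size Calculation) takes its variability from published healthy controls, of whom there were 40: "Values for healthy controls for 16S rRNA genes were median 411.73 gene copy number per mL, IQR 186.62-617.16". It assumes that the mean is close to the median and reaches an SD by "extrapolating an approximate value for standard deviation (34/25x225=306". It enters that SD, with a difference of 206 (half of the median), alpha 0.05 and power 0.8, into a "Sample size for a paired or single sample Student t test" calculation. The result is "Estimated minimum sample size = 20 pairs; Degrees of freedom = 19". The plan recruits 22 so that 20 complete, and section 3.5 replaces dropouts until 20 have completed.

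Section 9.1 does not say which two quantities form a pair. Elsewhere:

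- The primary objective in section 2.0 compares the lecithin diet with the control period and adds "Measured as responding to pre and post dietary treatment as gene copy number per ml".
- The secondary endpoints are "Changes in comparison to control (expressed as pre-post change per diet period").
- Section 3.3 has "4 study visits representing pre-post each diet treatment".
- Section 9.2 states "Data analysis will be performed using linear mixed models" but does not name the contrast to be tested.

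**The concern.** There are two weaknesses in the same input.

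The first is the conversion. No derivation is printed, but 34% is the normal probability within one SD on one side of the mean, and 25% is the probability between the median and a quartile. Multiplying a quartile distance by 34/25 is right only if probability accumulates evenly with distance. On the normal curve that the 34% implies, it does not. The plan also uses only the longer half of the IQR.

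The second is how the SD is used. It describes the spread between people measured once, yet it is entered as the SD of a within-person difference. The two are equal only at a particular within-person correlation, and that correlation depends on the contrast.

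The SD is the sole variability input to the sample size, so both the 20 pairs and the 80% rest on it.

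**Working it through.** **Inputs, all from section 9.1.** Median 411.73; quartiles 186.62 and 617.16; SD 306; difference 206 (0.5 × 411.73 = 205.9); alpha 0.05; 20 pairs. The section does not say whether alpha is two-sided. Two-sided is inferred here because the two-sided t test returns exactly 20 pairs, whereas a one-sided t test returns 16 and a two-sided normal approximation 18.

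**Reproducing the plan.** 34/25 × 225 = 306. Power of the paired t test comes from the noncentral t distribution with n − 1 degrees of freedom and noncentrality (206/SD) × √n. With SD 306 it is 79.3% at 19 pairs and 81.5% at 20. The stated 20 is therefore reproduced.

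**Checking 306 against the plan's own quartiles.** A normal distribution with SD 306 has an IQR of 2 × 0.6745 × 306 = 412.8, but the quoted IQR is 617.16 − 186.62 = 430.54. It would also put Φ(225/306) − 0.5 = 26.9% of values within 225 on one side, where a quartile distance should contain 25%.

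**Normal-theory SD.** 430.54/(2 × 0.6745) = 319.2.

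**Why 306 is still close.** Two departures partly cancel:

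- The factor is low: 1.36/1.4826 = 0.917.
- The half-width is high: the lower half is 411.73 − 186.62 = 225.11, against a mean half-width of 430.54/2 = 215.27, a ratio of 1.046.
- The product is 0.959, which matches 306/319.2 = 0.959.

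**Effect on power, difference 206:**

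| Basis for SD (factor 1.483) | SD | Power at 20 pairs |
|---|---|---|
| Whole IQR | 319.2 | 78.2% |
| Lower half, 225.11/0.6745 | 333.7 | 74.5% |
| Upper half, 205.43/0.6745 | 304.6 | 81.8% |

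With SD 319.2, 21 pairs give 80.3%. At 20 pairs, 80% power needs a difference of 0.6604 SD. That is 0.6604 × 319.2 = 210.8 copies/mL, and 210.8/411.73 = 51.2%.

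**Sampling error.** Under normality, an SD taken from the IQR of 40 people has a relative standard error of about 18%. One standard error either side of 319.2 is 260 to 378, for which power is 92% to 64%.

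**The contrast.** Write ρ for the within-person correlation, with equal variances and, where four values are used, one common ρ.

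- One post-diet value per diet: SD of the difference = 319.2 × √(2(1 − ρ)), which equals 319.2 at ρ = 0.5.
- Difference between two pre-post changes: SD = 2 × 319.2 × √(1 − ρ), which equals 319.2 at ρ = 0.75.

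The documents give no ρ, so the values below are assumptions that show the range (20 pairs):

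| ρ (assumed) | One value per diet: SD, power | Two changes: SD, power |
|---|---|---|
| 0.5 | 319.2, 78% | 451.4, 49% |
| 0.6 | 285.5, 86% | 403.7, 58% |
| 0.75 | 225.7, 97% | 319.2, 78% |

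At ρ = 0.25, one value per diet gives 61%. At ρ = 0.9, two changes give 99%. Power reaches 80% at ρ = 0.52 for the first contrast and 0.76 for the second.

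**The case against.** The strongest reply is that nothing in the trial turns on the conversion. The plan calls its SD approximate, 306 is within 4% of 319, and the sample size moves by one pair. Whether there is a shortfall at all depends on which part of the IQR is used: the upper half, with the correct factor, gives 305 and 81.8%. Sampling error in the source SD is more than four times the correction. Nor is 319 established as the true SD. A normal distribution with mean 411.73 and SD 319 puts about 10% of gene copy numbers below zero, which cannot occur, and 306 fares little better at about 9%. The unnamed contrast is the larger matter, and it is a design assumption rather than arithmetic.

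All of this is accurate, and it keeps the point minor. It does not remove it. Calling an input approximate covers uncertainty in the figure, not a factor that contradicts the quartiles printed beside it. If the plan's own half-width of 225 is kept and only the factor is corrected, power falls to 74.5%. Recruiting 22 does not restore 80%, because the target is 20 completers. The doubt about normality applies to both SDs, so the assumption should be stated. The range over ρ shows sensitivity, not a proven loss of power, but it does show why the contrast has to be named.

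**Conclusion.** The concern holds and is minor. The conversion in section 9.1 is not the normal-theory one. Under normality and using the whole IQR, the SD is about 319. At 20 pairs, power for a difference of 206 is then about 78%, 1.8 points below the stated 80%; equivalently, the increase detectable with 80% power is about 51% rather than 50%.

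These figures assume a two-sided 5% test, normality (which a median and IQR cannot confirm), and an SD of the analysed contrast equal to the between-person SD of the cited controls. The last assumption matters most. It holds at a correlation of 0.5 for one post-diet value per diet and 0.75 for a difference of changes, and the documents support neither. The arithmetic is secure; 319 as the true SD of the contrast is not.

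**What to change.** In section 9.1:

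- Replace the conversion, and the SD input that follows from it, with IQR/1.349 = about 319, and state that this assumes normality.
- Keep 20 completers. Then do one of two things. Either restate power for a difference of 206 as about 78%, changing every statement of 80% in the section so that they agree. Or keep 80% power and restate the detectable difference as about 211 copies/mL, an increase of about 51%. The second is the tidier edit.
- Add one sentence that names the contrast and its condition, for example: *This takes the SD of the analysed within-person contrast [one post-diet value per diet, or the difference between the two pre-post changes] as equal to the between-person SD of the cited controls; this needs a within-person correlation of 0.5 for the first or 0.75 for the second (equal variances, common correlation), and no correlation data were available.* Keep only the contrast that will be analysed.

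The cost is wording in one section. Sample size, recruitment and analysis do not change.

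### Section 9.1 uses a cross-sectional SD (306) as the SD of a paired difference, so 80% power with 20 pairs rests on an unstated correlation between visits

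*Combined protocol and SAP*

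**What the plan says.** Section 9.1 (Sample Size Calculation) takes its variability from one published data set: "Values for healthy controls for 16S rRNA genes were median 411.73 gene copy number per mL, IQR 186.62-617.16". These values come from 40 healthy controls. The plan treats the mean as close to the median and reaches its SD by "extrapolating an approximate value for standard deviation (34/25x225=306". It then gives the inputs "Alpha = 0.05; Power = 0.8; Difference of mean from zero = 206; Standard deviation = 306" and names the test: "Sample size for a paired or single sample Student t test". The result is 20 pairs with 19 degrees of freedom.

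The primary objective in section 2.0 is bacterial DNA in venous blood on the lecithin diet "in comparison to control period of low-emulsifier diet". The measure is described this way: "Measured as responding to pre and post dietary treatment as gene copy number per ml". Section 3.3 sets the schedule: "In total there will a baseline visit followed by 4 study visits representing pre-post each diet treatment". Each person therefore supplies four values (Days 8, 22, 29 and 43). The list of secondary endpoints is explicitly in terms of change from before to after each diet, compared with control. Section 9.2 plans linear mixed models but does not specify the diet term.

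**The concern.** A paired t test is driven by the SD of the within-person contrast. The 306 describes how single values differ across people, so it contains between-person, within-person and assay variation together. It can stand in for a contrast SD only under a particular correlation between a person's visits. No such correlation is stated, and no section supplies a within-person SD or an SD of differences from which to derive one.

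The contrast also matters. A difference between two post-diet values and a difference between two pre-post changes have different SDs at the same correlation, and section 9.1 does not say which it refers to. This calculation is the only justification given for 20 completers on the primary endpoint, so the stated 80% has no support within the plan.

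**Working it through.** **Inputs from section 9.1.** Difference 206 (50% of 411.73 is 205.9); SD 306; alpha 0.05; n = 20; df 19. Sidedness is not stated. Two-sided is assumed because it gives 20 pairs, while a one-sided t test gives 16.

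**1. Reproduce the plan's figure.** Noncentral-t power with noncentrality (206/306) × √20 gives 81.5% at n = 20 and 79.2% at n = 19. The minimum is 20 pairs, as stated. This confirms that 306 was entered as the SD of the paired difference.

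**2. Check the conversion to 306.** The 225 is the lower half of the interquartile range: 411.73 − 186.62 = 225.11. The factor 34/25 = 1.36 scales a quartile distance to one SD in proportion to the percentages. Under normality the factor is 1/0.6745 = 1.483.
- Whole range: (617.16 − 186.62)/1.349 = 319.
- Lower half: 225.11/0.6745 = 334.
- Upper half: 205.43/0.6745 = 305.

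Used exactly as the plan uses 306, an SD of 319 gives 78% power at n = 20 (21 pairs for 80%), and 334 gives 75% (23 pairs).

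**3. From per-visit SD to contrast SD.** Let S be the SD at each visit and ρ the correlation between any two visits of the same person, with equal variances and equal correlations assumed.
- Post-diet difference (two values): S × √(2(1 − ρ)). This equals S only when ρ = 0.5.
- Difference of pre-post changes (four values): 2S × √(1 − ρ). This equals S only when ρ = 0.75.

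A mixed model does not remove the distinction. A generalised least squares check (20 people, assumed 10 per sequence, four visits, free visit means, S = 306, ρ = 0.5) gives a contrast SD of 306 if the diet effect enters only at post-diet visits. If the diets may also differ at pre-diet visits, it gives 433. These match the two formulas.

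**4. Correlation needed for 80%.** At n = 20 the contrast SD must not exceed 311.9. With S = 306 that requires:
- 1 − (311.9/306)²/2 = 0.48 for the post-diet difference;
- 1 − (311.9/306)²/4 = 0.74 for the difference of changes.

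With S = 319 the same formulas give 0.52 and 0.76.

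**5. Power at n = 20 over a range of ρ.** The documents give no ρ, so the range is an assumption. Difference 206, two-sided 0.05, df 19.

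| ρ | Post-diet, S = 306 | Post-diet, S = 319 | Changes, S = 306 | Changes, S = 319 |
|---|---|---|---|---|
| 0 | 52% | 49% | 30% | 28% |
| 0.25 | 65% | 61% | 38% | 35% |
| 0.5 | 81% | 78% | 52% | 49% |
| 0.75 | 98% | 97% | 81% | 78% |
| 0.9 | >99% | >99% | >99% | 99% |

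**The case against.** The strongest reply is that no error in the number 20 has been shown. With no paired data cited, entering a cross-sectional SD amounts to assuming a correlation of 0.5 for a two-measurement difference, and section 9.1 does say that its SD is approximate. It is right that no shortfall is shown. But the disclosed approximation concerns reading an SD from quartiles, not turning a between-person SD into a paired one. A correlation of 0.5 would also not give 80% for a difference of changes.

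A second reply is that the planned mixed model can avoid the extra variance of change scores. It can, if the diet effect enters only at post-diet visits, but section 9.2 does not say so. The model would also have more residual degrees of freedom than the paired test: 80 observations − 20 people − 3 visit terms − 1 diet term = 56. Power at ρ = 0.5 with SD 306 is then about 84% rather than 81.5%. That is correct but small beside the effect of ρ or of the contrast.

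A third reply is that the upper half of the interquartile range gives 305, so 306 is not far off. That is fair. The conversion is a minor matter compared with the correlation, and the quartiles' asymmetry makes any normal-theory SD approximate.

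A reader might infer that the trial is underpowered, or that more participants are needed. The documents do not support either. With high within-person correlation, power exceeds 80% for both contrasts. A reader might also take the change contrast as settled. The pre-post wording of the primary objective points that way, but the explicit definition as change belongs to the secondary endpoints and does not formally govern the primary.

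**Conclusion.** The point stands as an unsupported input, not as proof of too small a sample. The stated 80% for 20 pairs holds only if the correlation between visits is about 0.5 (post-diet difference) or about 0.75 (difference of changes, the contrast that sections 2.0 and 3.3 more naturally suggest). Neither value is stated or justified. At a correlation of 0.5, the choice of contrast alone moves power from 81% to 52% with the plan's SD. Correcting the quartile conversion costs a further three percentage points or so at that correlation. True power may be above or below 80%, and the plan gives no basis to tell which.

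These figures assume a two-sided 5% test, equal variances and equal correlation between all visits. They would shift if correlations within a diet period differ from those between periods. Section 9.1 also frames the aim as "The sample size chosen to give 80% power to exclude 50% increase in circulating bacterial DNA". When a 50% increase would count as excluded is a separate question and is not part of this point.

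**What to change.** Revise section 9.1 in three ways:

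1. Name the contrast that the calculation refers to, either a post-diet difference or a difference of pre-post changes, and keep it consistent with the primary objective and with the diet term of the mixed model in section 9.2.
2. Describe the published figure as a per-visit SD, correct the quartile conversion (about 319, with 334 as a sensitivity value), and give the contrast SD as SD × √(2(1 − ρ)) or 2 × SD × √(1 − ρ) accordingly.
3. Replace the unconditional 80% with power at n = 20 over a wide range of ρ, labelled as an assumption. With SD 319 and ρ of 0, 0.25, 0.5, 0.75 and 0.9, the entries are those in the S = 319 columns of the table above. If the study team has repeat measurements that support a narrower range, cite them.

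The cost is a few sentences or one short table. The number of participants, the design and the data collection do not change. The drawback is that the stated power becomes conditional and may look less favourable.
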